**Veliparib Dose Calculation (Capsules) During Maintenance Chemotherapy**

Dose Level 1: 25 mg/m^2/dose PO BID			
BSA range (m^2)	Total Daily Dose (mg)	A.M. Dose (mg)	P.M. Dose (mg)
0.50–0.69	30	20	10
0.70–0.90	40	20	20
0.91–1.09	50	30	20
1.10–1.29	60	30	30
1.30–1.49	70	40	30
1.50–1.69	80	40	40
1.70–1.89	90	50	40
1.90–2.10	100	50	50
2.11–2.30	110	60	50
2.31–2.50	120	60	60

Dose Level -1: 20 mg/m^2/dose PO BID			
BSA range (m^2)	Total Daily Dose (mg)	A.M. Dose (mg)	P.M. Dose (mg)
0.50–0.69	20	10	10
0.70–0.90	30	20	10
0.91–1.12	40	20	20
1.13–1.37	50	30	20
1.38–1.62	60	30	30
1.63–1.87	70	40	30
1.88–2.12	80	40	40
2.13–2.37	90	50	40
2.38–2.5	100	50	50

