#### **Veliparib: PO**

Days: 1–5

Dose: 25 mg/m^2/dose BID (Total Daily Dose: 50 mg/m^2/day)

Veliparib will be given twice daily, and the morning (AM) dose should be given 60–120 minutes prior to the daily dose of temozolomide. Veliparib and temozolomide will be given on Days 1–5.

Alternatively, temozolomide may be given with the PM dose of veliparib, as long as:

- 1) temozolomide is given around the same time consistently every day
- 2) veliparib is administered 60-120 minutes prior to temozolomide to optimize the synergistic activity between the two agents.

Administer veliparib orally without regards to meals.

- Veliparib Oral Solution: Do not mix veliparib oral solution directly in apple/grape juice; however, patients can drink apple juice or grape juice after the dose. Do NOT drink orange juice, other citrus based juices, or grapefruit juice while taking veliparib oral solution (Days 1–5).
- Veliparib Capsules: Swallow capsules whole; do not chew or break.

For patients taking the oral solution, veliparib doses  $<$  30 mg should be rounded to the nearest 1 mg [0.1 mL] (e.g., 11.4 mg to be rounded to 11 mg and 19.5 mg to be rounded to 20 mg). For doses between 30 to 100 mg, round oral solution doses to the nearest 2 mg [0.2 mL] (e.g., 45.4 mg should be rounded to 46 mg).

Doses of capsule formulation should be rounded to the nearest 10 mg and can be divided unevenly if necessary to achieve a total daily dose (e.g., 30 mg in AM and 20 mg in PM). See suggested capsule dosing tables in [Appendix VII](#).

Patient veliparib wallet cards are provided in the [Appendix VI](#).

**Note:** Patients are not allowed to take a combination of capsules and the oral solution of veliparib for an individual dose.

If emesis occurs within 15 minutes of administration of veliparib, the dose should be repeated once. A missed dose will not be made up, but the missed dose and reason for missing the dose should be recorded in the patient's record.

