##### **Veliparib: PO**

Days: 1–5

Dose: 25 mg/m^2/dose BID (Total Daily Dose: 50 mg/m^2/day)

Veliparib will be given twice daily, and the morning (AM) dose should be given 60–120 minutes prior to the daily dose of temozolomide. Veliparib and temozolomide will be given on Days 1–5.

Alternatively, temozolomide may be given with the PM dose of veliparib, as long as:

- 1) temozolomide is given around the same time consistently every day
- 2) veliparib is administered 60–120 minutes prior to temozolomide to optimize the synergistic activity between the two agents.

Administer veliparib orally without regards to meals.

- Veliparib Oral Solution: Do not mix veliparib oral solution directly in apple or grape juice; however, patients can drink apple juice or grape juice after the dose. Do NOT drink orange juice, other citrus based juices, or grapefruit juice while taking veliparib oral solution (Days 1-5 of each cycle).
- Veliparib Capsules: Swallow capsules whole; do not chew or break.

For patients taking the oral solution, veliparib doses  $<$  30 mg should be rounded to the nearest 1 mg [0.1 mL] (e.g., 11.4 mg to be rounded to 11 mg and 19.5 mg to be rounded to 20 mg). For doses between 30 to 100 mg, round oral solution doses to the nearest 2 mg [0.2 mL] (e.g., 45.4 mg should be rounded to 46 mg).

Doses of capsule formulation should be rounded to the nearest 10 mg and can be divided unevenly if necessary to achieve a total daily dose (e.g., 30 mg in AM and 20 mg in PM). See suggested capsule dosing tables in [Appendix VII](#).

Patient veliparib wallet cards are provided in the [Appendix VI](#).

**Note:** Patients are not allowed to take a combination of capsules and the oral solution of veliparib for an individual dose.

If emesis occurs within 15 minutes of administration of veliparib, the dose should be repeated once. A missed dose will not be made up, but the missed dose and reason for missing the dose should be recorded in the patient's record.

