## 5.0 DOSE MODIFICATIONS FOR TOXICITIES

### 5.1 Dose Levels Tables

The starting dose level of veliparib is 65 mg/m^2/dose BID during Chemoradiotherapy and 25 mg/m^2/dose BID during Maintenance therapy.

**Table 1.** Dose Levels for Veliparib during Chemoradiotherapy

Dose Level	Veliparib dose (mg/m  /dose BID)
-2	35 mg/m  /dose BID
-1	50 mg/m  /dose BID
1*	65 mg/m^2/dose BID

\*Starting dose level

**Table 2.** Dose Levels for Veliparib and Temozolomide during Maintenance Therapy

Dose Level	Veliparib Dose	Temozolomide Dose
-1	20 mg/m  /dose BID	135 mg/m  /day
1*	25 mg/m^2/dose BID	135 mg/m^2/day

\*Starting dose level

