**APPENDIX VII: SUGGESTED VELIPARIB CAPSULE DOSING TABLES**

**Veliparib Dose Calculation (Capsules) During Chemoradiotherapy**

Dose Level 1: 65 mg/m^2/dose PO BID			
BSA range (m^2)	Total Daily Dose (mg)	A.M. Dose (mg)	P.M. Dose (mg)
0.50–0.57	70	40	30
0.58–0.65	80	40	40
0.66–0.73	90	50	40
0.74–0.80	100	50	50
0.81–0.88	110	60	50
0.89–0.96	120	60	60
0.97–1.03	130	70	60
1.04–1.11	140	70	70
1.12–1.19	150	80	70
1.2–1.26	160	80	80
1.27–1.34	170	90	80
1.35–1.42	180	90	90
1.43–1.49	190	100	90
1.5–1.57	200	100	100
1.58–1.65	210	110	100
1.66–1.73	220	110	110
1.74–1.8	230	120	110
1.81–1.88	240	120	120
1.89–1.96	250	130	120
1.97–2.03	260	130	130
2.04–2.11	270	140	130
2.12–2.19	280	140	140
2.2–2.26	290	150	140
2.27–2.34	300	150	150
2.35–2.42	310	160	150
≥ 2.43	320	160	160

Dose Level -1: 50 mg/m^2/dose PO BID			
BSA range (m^2)	Total Daily Dose (mg)	A.M. Dose (mg)	P.M. Dose (mg)
0.50–0.54	50	30	20
0.55–0.65	60	30	30
0.66–0.74	70	40	30
0.75–0.84	80	40	40
0.85–0.94	90	50	40
0.95–1.05	100	50	50
1.06–1.15	110	60	50
1.16–1.25	120	60	60
1.26–1.34	130	70	60
1.35–1.45	140	70	70
1.46–1.54	150	80	70
1.55–1.65	160	80	80
1.66–1.74	170	90	80
1.75–1.85	180	90	90
1.86–1.94	190	100	90
1.95–2.05	200	100	100
2.06–2.14	210	110	100
2.15–2.25	220	110	110
2.26–2.34	230	120	110
2.35–2.44	240	120	120
2.45–2.5	250	130	120

Dose Level -2: 35 mg/m^2/dose PO BID			
BSA range (m^2)	Total Daily Dose (mg)	A.M. Dose (mg)	P.M. Dose (mg)
0.50–0.64	40	20	20
0.65–0.78	50	30	20
0.79–0.92	60	30	30
0.93–1.07	70	40	30
1.08–1.21	80	40	40
1.22–1.35	90	50	40
1.36–1.5	100	50	50
1.51–1.64	110	60	50
1.65–1.78	120	60	60
1.79–1.92	130	70	60
1.93–2.07	140	70	70
2.08–2.21	150	80	70
2.22–2.35	160	80	80
2.36–2.50	170	90	80

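### Over two narrow BSA bands, the maintenance Dose Level -1 veliparib capsule table departs from the stated dose level and the rounding rule; this may be deliberate, but no section says so.

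*Combined protocol and SAP*

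**What the plan says.** Section 5.1, Table 2 ("Dose Levels for Veliparib and Temozolomide during Maintenance Therapy"), sets veliparib at Dose Level -1 to "20 mg/m 2 /dose BID". The matching table in Appendix VII carries the same figure in its header: "Dose Level -1: 20 mg/m".

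Section 4.4.3 (Cycle 1) and Section 4.5.3 (Cycles 2–10) give one rounding rule for capsules: "Doses of capsule formulation should be rounded to the nearest 10 mg and can be divided unevenly if necessary to achieve a total daily dose". Both sections then point to Appendix VII, as does the overview in Section 4.1.2.

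The first two rows of the Dose Level -1 maintenance table give BSA range, total daily dose, morning dose and evening dose:

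- "0.50–0.69 20 10 10"
- "0.70–0.90 30 20 10"

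The Dose Level 1 maintenance table directly above has the same first two BSA ranges, with totals of 30 and 40 mg/day. The appendix is titled "SUGGESTED VELIPARIB CAPSULE DOSING TABLES".

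**The concern.** A table built on 40 mg/m² per day should change its capsule total at different BSA values from a table built on 50 mg/m² per day. Here the first two ranges coincide, and from the third row onward they differ. In part of those two ranges, a pharmacist who works from the dose level and the rounding rule gets one daily dose, and one who reads the table gets another.

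A patient reaches this dose level only after a dose-modifying toxicity. Under Sections 5.3.1.2 and 5.3.2.2, a further such toxicity at this level can end protocol therapy. The dose meant at that point should be unambiguous.

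**Working it through.** **Inputs.** Dose per administration d: 25 mg/m² (Dose Level 1) or 20 mg/m² (Dose Level -1), from Table 2 and the Appendix VII headers. Rounding: nearest 10 mg, applied to the daily total because the rule allows unequal morning and evening doses to reach it. BSA ranges and listed totals: Appendix VII.

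**Formula.** Calculated daily dose = 2 × d × BSA. Rule dose = that value rounded to the nearest 10 mg, with exact ties accepted either way. Relative gap = (listed − calculated) / calculated. BSA was taken in steps of 0.01 m².

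**Does the rule reproduce the plan's tables?** Appendix VII holds five veliparib capsule tables with 26 + 21 + 14 + 10 + 9 = 80 rows. The open-ended top row of the first chemoradiotherapy table was checked up to 2.50 m². The rule reproduces 78 rows at every BSA. The two exceptions are rows 1 and 2 of the Dose Level -1 maintenance table, each over part of its range.

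**Row 1 (0.50–0.69 m², 20 mg listed).** The rule total changes from 20 to 30 mg between 0.62 (40 × 0.62 = 24.8) and 0.63 (40 × 0.63 = 25.2). The table places the change between 0.69 and 0.70.

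**Row 2 (0.70–0.90 m², 30 mg listed).** The rule total changes from 30 to 40 mg between 0.87 (34.8) and 0.88 (35.2). The table places the change between 0.90 and 0.91.

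| BSA (m²) | Calculated (mg/day) | Listed | Rule | Gap from calculated | Dose Level 1 table |
|---|---|---|---|---|---|
| 0.63 | 25.2 | 20 | 30 | −20.6% | 30 |
| 0.69 | 27.6 | 20 | 30 | −27.5% | 30 |
| 0.88 | 35.2 | 30 | 40 | −14.8% | 40 |
| 0.90 | 36.0 | 30 | 40 | −16.7% | 40 |

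Seven of the 20 BSA steps in row 1 and three of the 21 in row 2 are affected.

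**What rounding alone does.** Among entries that follow the rule at this level, the largest gap is at BSA 0.62: (20 − 24.8) / 24.8 = −19.4%. All of the second band lies inside that figure. All of the first band lies outside it, by at most 27.5 − 19.4 = 8.1 percentage points.

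**Alternative rules.** Rounding each dose separately fits row 1 but fails four of the nine rows of this table, including row 2. Always rounding down fits row 1 but not the others; for example, 0.70 m² gives 28 mg, which would become 20, and the table lists 30.

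**Comparison with Dose Level 1.** At all ten affected BSA values the rule dose for Dose Level -1 (30 mg, then 40 mg) equals the total in the Dose Level 1 table. At no other BSA from 0.50 to 2.50 m² does this happen. As printed, the Dose Level -1 total is below the Dose Level 1 total throughout.

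**The case against.** The strongest reply is that the cut-points are intended. Temozolomide stays at 135 mg/m² per day at both maintenance levels (Table 2), so veliparib is the only drug lowered when a patient moves to Dose Level -1. Under the rule, a child in either band would keep the same capsule total after the reduction. Keeping the Dose Level 1 cut-points for the two smallest ranges avoids that, and the departures occur at exactly the values where it would arise and nowhere else. The chemoradiotherapy dose steps produce no such ties, and those tables follow the rule. This explanation fits the pattern completely.

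It remains an inference. Sections 4.4.3, 4.5.3 and 5.1 and Appendix VII mention no exception. A reader might equally infer that the two ranges were carried over by mistake from the table above, so that the rows are errors and children in these bands would be underdosed. The documents do not support that reading either: identical ranges are consistent with both explanations, and nothing shows which was meant.

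Three further objections stand. Rounding to 10 mg is coarse at small BSA, so the whole 28% should not be read as the cost of the departure. The tables are suggestions, and they do not govern the oral solution, which is rounded to 1 mg below 30 mg. The reach is very small. Stratum 1 is closed and Stratum 2 plans 30 patients. Section 2.4 reports no IDH mutation among 23 children under 14, and Section 9.2 gives historical controls aged 11.7–28 years (median 16.9). Eligibility does start at age 3, so such a patient is possible. The patient would also have to be on capsules, at Dose Level -1, and within one of the two bands.

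**Conclusion.** The inconsistency is real and minor. Over BSA 0.63–0.69 and 0.88–0.90 m², the table and the text give different daily capsule doses at the same dose level. The listed dose is 21–28% below the calculated dose in the first band and 15–17% below in the second; rounding alone gives gaps of up to about 19%.

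This rests on reading the rounding rule as applying to the daily total, which the other 78 rows bear out, and on BSA recorded to two decimals. The documents do not settle whether the departure is deliberate.

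A reader might go on to infer that efficacy or safety conclusions are at risk. The documents do not support that, given how few patients could be in these bands at this dose level. The point belongs among minor corrections.

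**What to change.** The sponsor should reconcile the rounding text in Sections 4.4.3 and 4.5.3 and the dose level in Table 2 of Section 5.1 with the first two rows of the Dose Level -1 maintenance table in Appendix VII. There are two ways to do so: bring the text and the table into agreement, or keep both and add a note to the table stating the exception and its reason. The sponsor's pharmacist should confirm which cut-points were intended. This review does not say which dose should stand.

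The cost is a footnote or a revision of two appendix rows at the next amendment. Sample size, data collection and the planned analyses do not change.

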**APPENDIX VIII: SUGGESTED TEMOZOLOMIDE CAPSULE DOSING TABLES**

**Temozolomide Dosing Tables**

135 mg/m  /day					
Min BSA (m  )	Max BSA (m  )	Daily TMZ Dose (mg)	Min BSA (m  )	Max BSA (m  )	Daily TMZ Dose (mg)
0.2	0.2	25	1.36	1.38	185
0.21	0.24	30	1.39	1.42	190
0.25	0.27	35	1.43	1.46	195
0.28	0.31	40	1.47	1.49	200
0.32	0.35	45	1.5	1.53	205
0.36	0.38	50	1.54	1.57	210
0.39	0.42	55	1.58	1.61	215
0.43	0.46	60	1.62	1.64	220
0.47	0.49	65	1.65	1.68	225
0.5	0.53	70	1.69	1.72	230
0.54	0.57	75	1.73	1.75	235
0.58	0.61	80	1.76	1.79	240
0.62	0.64	85	1.8	1.83	245
0.65	0.68	90	1.84	1.87	250
0.69	0.72	95	1.88	1.9	255
0.73	0.75	100	1.91	1.94	260
0.76	0.79	105	1.95	1.98	265
0.8	0.83	110	1.99	2.01	270
0.84	0.87	115	2.02	2.05	275
0.88	0.9	120	2.06	2.09	280
0.91	0.94	125	2.1	2.12	285
0.95	0.98	130	2.13	2.16	290
0.99	1.01	135	2.17	2.2	295
1.02	1.05	140	2.21	2.24	300
1.06	1.09	145	2.25	2.27	305
1.1	1.12	150	2.28	2.31	310
1.13	1.16	155	2.32	2.35	315
1.17	1.2	160	2.36	2.38	320
1.21	1.24	165	2.39	2.42	325
1.25	1.27	170	2.43	2.46	330
1.28	1.31	175	2.47	2.49	335
1.32	1.35	180	2.50	2.50	340

**APPENDIX IX: POSSIBLE DRUG INTERACTIONS**

**Temozolomide**

Some drugs, food, and supplements may interact with temozolomide. Examples include:

Drugs that may interact with temozolomide*

 
• Clozapine, leflunomide, natalizumab, tofacitinib, valproate products
 

Food and supplements that may interact with temozolomide**

 
• Echinacea
 

*\*Sometimes these drugs are used with temozolomide on purpose. Discuss all drugs with your doctor.*

*\*\*Supplements may come in many forms, such as teas, drinks, juices, liquids, drops, capsules, pills, or dried herbs. All forms should be avoided.*

***The list above does not include everything that may interact with your chemotherapy. Talk to your doctor before starting any new medications, over-the-counter medicines, or herbal supplements and before making a significant change in your diet.***

